Following completion of this initial baseline visit, participants will be randomized (1:1) to the intervention or control arm. Random assignment to condition will minimize the likelihood of bias in either condition. A study research assistant or staff member not involved in the actual therapy will hold the randomization scheme, which will be developed by the study biostatistician ([name]). Baseline characteristics for each group will be examined for significant differences.

The control condition will be a supportive therapy program that is matched to the intervention for number and length of sessions. A version of this intervention has been used in a randomized controlled trial evaluating the efficacy of a combined depression and adherence treatment intervention, on which [name] worked (R01MH084757). Basic principles of supportive psychotherapy will be followed, and the interventionist will facilitate discussion around what it is like to live with HIV as an aging woman. Sessions will be delivered by a study staff member (either in person or via Zoom) who will be thoroughly trained on the intervention or control condition material (e.g., predoctoral psychology intern, postdoctoral psychology fellow, junior psychologist). All group facilitators will receive supervision on a weekly or biweekly basis.

Participants will be given the opportunity to attend up to 3 make-up sessions (either in person or via Zoom) if they are unable to attend the originally scheduled session. For the control condition, makeup sessions will entail individual supportive psychotherapy. We will also allow participants to call into up to 3 group sessions by phone after having attended at least one session in-person. This will allow for more flexibility in scheduling and facilitate better overall attendance over the duration of the program. Additionally, participants in both the intervention and control groups will receive a schedule of all group sessions in order to minimize confusion about session dates and maximize efficiency of make-up scheduling.

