### **Data analytic plan.**

Quantitative data will be entered in an on-going fashion (into REDCap data management system), and will be analyzed using SPSS, "R", and QSR NVivo qualitative software, version 9, after being thoroughly checked and cleaned as appropriate. [name] has the full support of a biostatistician ([name]) for all statistical analyses. We will compile descriptive statistics to examine intervention acceptability and feasibility as described above, as well as to examine indicators of change on measures of various psychosocial outcomes. We will compare each outcome between groups using mixed model regression analyses, with subject as a random effect. Fixed covariates will include time in study (baseline, end of treatment, 3-month follow-up) and time since diagnosis. Other covariates, such as education, socioeconomic status, and history of exposure to traumatic events will also be considered. We will consider exploratory mediational and moderational analyses, based on procedures outlined by Hayes. We will assess adherence in the active treatment arm, in particular to determine if adherence is related to change in the primary outcome. We will perform exploratory multivariate analyses among the outcomes, including graphical methods and the calculation and testing of correlations and partial correlations. We will examine patterns in missing data in order to see if missingness is related to measured patient characteristics. We will adjust for missing data using multiple

imputation as appropriate. We will adjust for multiple comparisons using the method of Hothorn, Bretz and Westfall. Statistical analyses will be performed using “R” software.

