## STATISTICAL ANALYSIS PLAN

## Statistical Plan for Analyses

Power: PAR-14-182 states, "...the R34 should ... enhance the probability of reaching more definitive outcomes in a larger trial... by working out the details of the experimental protocols, including the assessment protocol, the...intervention protocol, as well as the comparison intervention protocol and randomization procedures; examining the feasibility of recruiting and retaining participants into the study conditions; ... collection of preliminary data regarding feasibility, acceptability, safety, tolerability, and target outcomes is appropriate. Given the limited sample sizes that can be supported under this...mechanism, proposing the use of a comparison group for conducting fully powered tests of outcomes (i.e., efficacy) or attempting to utilize the highly variable point estimate of an effect size for power calculations would not be appropriate." As stated in the specific aims, we aim to test the feasibility and acceptability of all study procedures as a primary goal; we will not attempt to use our data to estimate an effect size. We are interested in the sensitivity of our selected measures to detect change. Thus, as an exploratory outcome, we propose to examine the intervention effect of resilience and other secondary outcomes. We have conducted power calculations to ensure any lack of effect would be unrelated to power. We also explored current funded R34 studies of similar scope that are currently funded by NCCIH, and our sample size is well within the range of what is documented in these studies (e.g., 5R34AT008423, 1R34AT007935).

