Power calculations are based on samples of older, HIV-infected women when available. When data from older HIV-infected women were not available, data from samples of older women, women, or HIV-infected populations were used. We also examined data from community samples. We calculated power estimates for the primary outcome (resilience as measured by the CD-RISC) and for two of the secondary outcomes, depressive symptoms and health related quality of life. With respect to resilience, from Dodding et al., we estimate the standard deviation of change due to the intervention to be 11.8. With 30 patients per group, we will have 80% power to detect a change in resilience of 6.2 points or greater, in absolute value, based on a paired t-test at the 0.05 two-tailed significance level. We estimate the population mean and standard deviation to be approximately 76+/-13 for community-based controls, and 71.7+/-12.5 for a community-based sample of post-menopausal women with sub-clinical depression (N=401). A change of 6.2 points corresponds to approximately 1/2 of a standard deviation for both of these populations (i.e., an effect size of 0.5). Comparing the post-pre differences between treatment arms, we estimate that we will have 80% power to detect an absolute difference of 8.7 on the CD-RISC, based on a two-sample t-test at the 0.05 two-tailed significance level (an effect size of 0.7, which corresponds to a medium-large effect size.

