For depressive symptoms, Ickovics et al. reported that 42% of HIV seropositive women were depressed, based on reporting a CES-D score of >16 for 75% of more of study visits. Assuming that the population proportion of participants with elevated depressive symptoms in the placebo arm at the end of the study is 0.42, then with 30 participants per arm, we will have 80% power to detect that the corresponding treatment proportion is <0.12 or >0.76. For health related quality of life, Mrus et al. reported a mean for the overall health domain of HRQoL in women engaged in HIV treatment of 71.4, with a standard deviation of 13.8. Using this standard deviation, with 30 participants per arm, we will have 80% power to detect if the absolute mean between-group difference in this quality of life measure at the end of the study is 10.2 points or greater, based on a two-sample t-test at the 0.05 two-tailed significance level. In summary, we are confident that we can achieve a medium to large effect size across multiple outcomes with the proposed N.

**Analyses:** With respect to quantitative data, we will compare each outcome between groups using mixed- model regression analyses, with subject as a random effect. Fixed covariates will include time in study (baseline, end of treatment, 3 month follow-up) and time since diagnosis. Other covariates, such as education, socioeconomic status, and history of exposure to traumatic events will also be considered. We will consider exploratory mediational and moderational analyses, based on procedures outlined by Hayes. We will assess adherence in the active treatment arm, in particular to determine if adherence is related to change in the primary outcome. We will perform exploratory multivariate analyses among the outcomes, including graphical methods and the calculation and testing of correlations and partial correlations. We will examine patterns in missing data in order to see if missingness is related to measured patient characteristics. We will adjust for missing data using multiple imputation as appropriate. We will adjust for multiple comparisons using the method of Hothorn, Bretz and Westfall. Statistical analyses will be performed using “R” software.

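### The between-arm mixed model treats baseline as an outcome visit but states no arm-by-visit term, baseline adjustment or contrast to be reported

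*Combined protocol and SAP*

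**What the plan says.** The protocol's Data analytic plan states: "We will compare each outcome between groups using mixed model regression analyses, with subject as a random effect". The SAP's Analyses paragraph repeats this and adds: "Fixed covariates will include time in study (baseline, end of treatment, 3 month follow-up) and time since diagnosis". Education, socioeconomic status and trauma history are to be considered as further covariates. Arm is implied by the comparison between groups but is not listed. Neither section mentions an arm-by-visit interaction, the baseline value of the outcome, a constraint of equal baseline means, or the contrast and visit to be reported. Moderation analyses are only to be considered and are not described as arm by time.

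The SAP's power paragraphs use visit-specific contrasts, and these differ. For resilience (CD-RISC): "Comparing the post-pre differences between treatment arms, we estimate that we will have 80% power" for 8.7 points. For quality of life, the target is that the "absolute mean between-group difference in this quality of life measure at the end of the study is 10.2 points or greater". For depressive symptoms it is the proportion with elevated symptoms, also at study end. There is an end-of-treatment visit and a 3-month visit, and the SAP does not say which one ends the study.

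On missing data: "We will adjust for missing data using multiple imputation as appropriate". The imputation model is not given. On power: "We have conducted power calculations to ensure any lack of effect would be unrelated to power".

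**The concern.** When baseline is a level of the outcome's time factor, an arm main effect without an interaction pools a visit at which treatment cannot yet have acted. Under Study procedures and data collection, "Following completion of this initial baseline visit, participants will be randomized (1:1) to the intervention or control arm", so the expected arm difference at baseline is zero. Averaging that zero with the two later differences shrinks the estimate. A measure that responds to the intervention could then look unresponsive, and sensitivity to change is what Specific Aims and the SAP say they most want to learn from these outcomes. The 80% power figures would also belong to contrasts that the analysis text does not contain. As written, two analysts following the plan could report different quantities.

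**Working it through.** **Inputs.** From the SAP: 30 per arm, two-sided 0.05; CD-RISC SD of change 11.8 and difference 8.7; quality-of-life SD 13.8 and difference 10.2. Assumed, because the documents give neither: equal correlation ρ between visits, from 0.3 to 0.7, and no dropout. Power is by the noncentral t distribution.

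**1. The plan's own figures.**
- CD-RISC: SE = 11.8 × √(2/30) = 3.047; 8.7/3.047 = 2.86; power 80.2%.
- Quality of life: SE = 13.8 × √(2/30) = 3.563; 10.2/3.563 = 2.86; power 80.4%.

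Both reproduce.

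**2. What arm plus the listed terms would estimate.** With complete data, a random intercept and no interaction, the arm coefficient is the difference in subject means over the three visits, (D0 + D1 + D2)/3, with D0 = 0 in expectation.
- Effect d at both later visits: 2d/3. For 10.2 this is 6.8.
- Effect halved by 3 months: (d + d/2)/3 = d/2, or 5.1.
- Effect gone by 3 months: d/3, or 3.4.

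These fractions depend on neither the scale nor ρ. Simulated mixed models for the CD-RISC, including time since diagnosis, agree: for d = 8.7 the expected coefficient is 5.8, and 400 simulated trials averaged 5.93. The arm-by-visit model averaged 8.80.

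**3. Illustrative power for quality of life**, with 10.2 points at both post-baseline visits:
- Listed terms plus arm: coefficient 6.8, SE = 13.8 × √[(2/30)(1 + 2ρ)/3], 58 df.
- End of treatment adjusted for baseline: 10.2, SE = 13.8 × √[(2/30)(1 − ρ²)], 57 df.
- Post-pre change: 10.2, SE = 13.8 × √[(2/30) × 2(1 − ρ)], 58 df.

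At ρ = 0.5 the SEs are 2.909, 3.086 and 3.563, and the ratios of effect to SE are 2.34, 3.31 and 2.86.

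| ρ | Listed terms plus arm | Adjusted for baseline | Post-pre change |
|---|---|---|---|
| 0.3 | 72.9% | 83.9% | 66% |
| 0.4 | 67.8% | 86.7% | 73% |
| 0.5 | 63.3% | 90.1% | 80% |
| 0.6 | 59.2% | 94.0% | 88% |
| 0.7 | 55.5% | 97.6% | 95% |

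The first column is below the stated 80.4% for any ρ above 0.17. The baseline-adjusted column is above it throughout. The change contrast reaches it only from about ρ = 0.5, and at ρ = 0.3 it is below even the listed-terms model.

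**4. Participants seen only at baseline.** If 25% of each arm had no later visit (an assumed rate), a likelihood-based fit of the listed terms plus arm would give 0.57, 0.54 and 0.52 of a sustained effect at ρ = 0.3, 0.55 and 0.8. Imputation that includes arm and baseline would leave the expectation at two thirds, but the plan does not say what the imputation model contains.

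**The case against.** The covariate list is open: it omits arm itself and leaves others to be considered, so it cannot be read as a complete model. Specific Aims hypothesises greater improvements in the treatment arm, the CD-RISC power contrast is a post-pre difference, and every powered contrast is visit-specific. One arm-by-visit model could supply all the continuous ones. At a given visit, randomisation after baseline gives the change contrast and the plain arm difference the same expectation. Most analysts would add the interaction. All of this stands, and it limits the point to under-specification.

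The stakes are also modest. Feasibility and acceptability are the primary aim, outcome analyses are called purely exploratory, the SAP disclaims estimating an effect size, and no decision rule hangs on this coefficient. The descriptive work "to examine indicators of change on measures of various psychosocial outcomes" and the paired within-group calculation are untouched.

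A reader might go further and infer that CD-RISC power would fall to 51-56%. The documents do not support that figure. It needs a correlation obtained by combining the 11.8 SD of change with cross-sectional SDs of 12.5 and 13 from other samples: 1 − 11.8²/(2 × 12.5²) = 0.55 and 1 − 11.8²/(2 × 13²) = 0.59. With the SD of change held at 11.8, power runs from 86% to 37% as ρ goes from 0.3 to 0.7, so even the direction against 80% is unsettled. The source means of 76 and 71.7 also lie outside the 0-40 range the protocol gives for its version of the scale. The CD-RISC power figures for the listed-terms model should carry no weight.

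**Conclusion.** The point holds as an incomplete specification. Both statements of the model make baseline an outcome visit and leave out the interaction, any baseline adjustment and the reported contrast. The power paragraphs suggest contrasts but do not fix one, because they use both change and end-of-study differences and leave the end visit undefined.

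It would be wrong to conclude that the trial will report two thirds of its effect. That fraction belongs to one reading, arm added to the listed terms and nothing else, and is exact only for a sustained effect, complete data and equal expected baseline means. On that reading the coefficient matches none of the powered contrasts. The quality-of-life illustration (73% to 56% against 80%) rests on the SAP's SD of 13.8 and on assumed correlations.

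The consequence is confined to the exploratory between-arm analyses, including what they show about the measures' sensitivity to change, and to the SAP's assurance that a null result would not reflect low power. The correction costs nothing in data and can gain precision, so it is worth making.

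**What to change.** In the protocol's Data analytic plan and the SAP's Analyses paragraph, write the model out: post-baseline visits as the response; arm, visit, arm-by-visit, the baseline value of the outcome and time since diagnosis as fixed effects; and a random subject effect. An equivalent longitudinal model with a common baseline mean would also do. Report the arm difference at each post-baseline visit with a 95% CI, and have the sponsor name the main visit in advance. State which visit the quality-of-life power statement means by study end. Include arm, visit and baseline in any imputation model.

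Stating only the arm-by-visit term and a named contrast would remove the dilution. If that contrast is post-pre change, however, it would not secure 80% for quality of life at the lower correlations (66% at 0.3, 73% at 0.4), which is why baseline adjustment is preferred.

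The cost is wording in two places. The baseline value of each repeated outcome is already collected.

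### The 80% power figures are for single unadjusted tests, but the plan adjusts the outcome comparisons for multiplicity over a family it never defines

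*Combined protocol and SAP*

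**What the plan says.** The Power text of the SAP (Statistical Plan for Analyses) takes CD-RISC as the primary outcome for power: "we estimate the standard deviation of change due to the intervention to be 11.8". Between arms, "we will have 80% power to detect an absolute difference of 8.7 on the CD-RISC". The test behind that figure carries no multiplicity adjustment; it is described as "based on a two-sample t-test at the 0.05 two-tailed significance level". The within-arm figure of 6.2 points is also "based on a paired t-test at the 0.05 two-tailed significance level". For health-related quality of life it gives 10.2 points (SD 13.8) on the same basis. For depressive symptoms it gives detectable proportions of 0.12 or 0.76 against 0.42, with no significance level stated.

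The Analyses paragraph that follows, and the protocol's Data analytic plan, cover all outcomes: "We will compare each outcome between groups using mixed model regression analyses, with subject as a random effect". Both add: "We will adjust for multiple comparisons using the method of Hothorn, Bretz and Westfall". Neither says which comparisons form the family, how many there are, what error rate is held, or whether CD-RISC stands outside. The power text does not mention the adjustment.

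The SAP also gives the power calculations a purpose. They are meant to guarantee that a null finding could not be put down to low power, and the power section closes by expressing confidence over several outcomes.

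**The concern.** A multiplicity adjustment raises the critical value each test must exceed. Power computed at an unadjusted 0.05 then does not describe the adjusted test. The gap matters here because the SAP itself relies on the power figures to interpret a null result, and the data are meant to inform a full-scale trial. An adjusted non-significant CD-RISC or quality-of-life result would be read against a power that the test did not have.

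The undefined family is a second difficulty. The cited method acts on contrasts of fitted models, and the plan fits one model per outcome. Adjusting only across visits within an outcome leaves the outcomes uncontrolled against one another; adjusting across outcomes costs much more power. As written, the choice could be made after the data are seen.

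**Working it through.** **Inputs from the documents.** 30 per arm; CD-RISC difference 8.7, SD 11.8; quality-of-life difference 10.2, SD 13.8; depression proportions 0.42 against 0.12 or 0.76; two-sided 0.05; post-baseline assessments at end of treatment and 3 months.

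**Assumptions of this check.** Family size k; equal correlation of 0.3 to 0.7 between test statistics; single-step max-t adjustment with 58 degrees of freedom, as an approximation to the cited method. The documents give none of these.

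**1. Reproduce the stated figures.** Noncentrality = difference / (SD × √(2/30)); power = P(noncentral t on 58 df > critical value), with unadjusted critical value 2.002.
- CD-RISC: 8.7 / (11.8 × 0.2582) = 2.856, power 80.2%.
- Quality of life: 10.2 / (13.8 × 0.2582) = 2.863, power 80.4%.
- Depression, unpooled normal formula at an assumed 0.05: 0.30 / √((0.42×0.58 + 0.12×0.88)/30) = 2.781, and 2.781 − 1.960 gives 79.4%. For 0.76: 0.34 / √((0.42×0.58 + 0.76×0.24)/30) = 2.853, giving 81.4%.

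So the stated 80% reproduces, at an unadjusted 0.05.

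**2. Candidate families.**
- k = 2: the two post-baseline visits of one outcome.
- k = 3: the three outcomes for which power is given.
- k = 8–9: the shorter list in Specific Aims (resilience, depressive symptoms, anxiety, social support, quality of life, viral load, symptom burden, cognitive and physical status).
- k = 16: the measures described under Assessment instruments: 2 under Resilience, 9 psychosocial, and 5 HIV/physical (engagement in care, adherence, viral load, symptom burden, cognitive status), one test each.

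**3. Power after adjustment.** Simulated 95th percentile of the maximum |t|, then the formula in step 1.

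| k | Critical value | Power at 8.7 (CD-RISC) | CD-RISC difference for 80% | Quality-of-life difference for 80% |
|---|---|---|---|---|
| 1 | 2.00 | 80.2% | 8.7 | 10.2 |
| 2 | 2.23–2.29 | 72–73% | 9.4–9.5 | 11.0–11.2 |
| 3 | 2.36–2.44 | 66–69% | 9.8–10.0 | 11.4–11.7 |
| 8–9 | 2.62–2.83 | 51–59% | 10.6–11.2 | 12.4–13.1 |
| 16 | 2.79–3.03 | 44–53% | 11.1–11.9 | 13.0–13.9 |

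Bonferroni gives 71.0%, 65.2% and 41.8% for k = 2, 3 and 16. At correlation 0.9, two tests reach about 76% and sixteen about 63%. Each of these is below 80%.

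**4. Adjustment within outcome only.** With each of 16 outcomes held at 5%, the chance of at least one false positive is 1 − 0.95^16 = 56% if the outcomes are independent, and about 26–46% at correlation 0.7 to 0.3.

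**5. Cost of exempting CD-RISC.** 16 outcomes × 2 visits − 1 = 31 remaining contrasts, or 30 if MOCS-A is collected only at baseline and post-treatment, as its own description says. With roughly 30 in one family, quality-of-life power at 10.2 points is about 37–48%, and the detectable difference is about 13.5–14.6.

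**The case against.** The strongest reply is that Specific Aims makes feasibility and acceptability the primary aim and calls the outcome analyses exploratory. The funding text quoted in the SAP also discourages fully powered outcome tests, so no trial decision hangs on an adjusted p-value. That stands, and it limits the severity. It does not remove the conflict, because the same SAP section uses the power figures to rule out low power as the explanation for a null result.

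Three stronger readings are tempting and not supported.
- A reader might infer that the planned tests have 44–73% power. Those figures come from assumed families and correlations: two tests correlated 0.9 give about 76%, Bonferroni over sixteen gives about 42%, and more contrasts would give less. Some outcomes, such as viral suppression and cognitive impairment, are binary, so a t-based family is only approximate. Covariates or repeated measures in the mixed model could recover some power, but the documents give no figure.
- A reader might infer that a stated property must fail however the adjustment is applied. If CD-RISC, which the SAP calls primary for power, were tested alone at 0.05, its 80% would stand. No sentence says this, but none excludes it.
- A reader might take 56% as the false-positive rate under within-outcome adjustment. It needs independent outcomes; at the correlations used for the power figures it is 26–46%.

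**Conclusion.** The mismatch is real and textual. The stated 80% holds at an unadjusted two-sided 0.05, the plan adjusts, and no comparison is exempted. Every outcome tested inside an adjusted family of two or more has less than the stated power under the adjustments examined. How much less cannot be fixed from the documents; the illustrations run from a few percentage points to nearly half of the stated power. The conclusion that power falls rests only on the text. The sizes rest on the assumed family, correlation and single-step rule.

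The point should be corrected but is not critical. What fails is the SAP's assurance about null results and its confidence over several outcomes, not the feasibility aim.

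**What to change.** In the SAP's Analyses paragraph and the protocol's Data analytic plan, state the family and the error rate held over it. If the family spans outcomes, say how the method is applied across separately fitted models. Then choose one of two routes.

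(a) Name the CD-RISC between-arm contrast at post-treatment as the single unadjusted 0.05 test to which the 80% refers. Restate the quality-of-life and depression power, or their detectable differences, at the adjusted level. The last step of the working shows how far the quality-of-life figures move if all remaining contrasts form one family.

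(b) State that all power figures are per-test and unadjusted, and report the other outcomes descriptively, with estimates and intervals.

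Under either route, qualify the Power sentence that excludes low power as a reason for a null result, and the closing statement of confidence over several outcomes. While editing, put the CD-RISC point values on the scale in use: the power text cites means of 71.7 and 76, but the instrument is described as ten items scored 0 to 40. The CD-RISC point values in the working carry the same scale problem.

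The cost is a few sentences and some less favourable figures. Sample size, visits and conduct do not change.
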